**7.1.2.1 Daratumumab Dose Delays Due to AEs**

The study treatment must be held if any of the following criteria below are met, to allow for recovery from toxicity. The criteria for a dose delay are:

- Grade 4 hematologic toxicity, except for grade 4 lymphopenia
- Grade 3 or higher thrombocytopenia
- Febrile neutropenia
- Neutropenia with infection, of any grade
- Grade 3 or higher non-hematologic toxicities with the following exceptions:
  - Grade 3 nausea that responds to antiemetic treatment within 7 days
  - Grade 3 vomiting that responds to antiemetic treatment within 7 days
  - Grade 3 diarrhea that responds to antidiarrheal treatment within 7 days
  - Grade 3 fatigue that was present at baseline or that lasts for <7 days after the last administration of daratumumab
  - Grade 3 asthenia that was present at baseline or that lasts for <7 days after the last administration of daratumumab

Administration of daratumumab may be restarted upon recovery from toxicity to Grade 2 or baseline, with the exception that Grade 2 laryngeal edema or Grade 2 bronchospasm must be fully recovered.

If daratumumab administration does not commence within the prespecified window (Table 7.1.2-1) of the scheduled administration date, then the dose will be considered a missed

dose. Administration may resume at the next planned dosing date. A missed dose will not be made up.

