### **8.1.1 Nivolumab Discontinuation Criteria**

Nivolumab treatment should be permanently discontinued for the following:

- Any Grade 2 drug-related uveitis, eye pain, or blurred vision that does not respond to topical therapy and does not improve to Grade 1 severity within the Re-Treatment Period OR requires systemic treatment
- Any Grade 3 non-skin, drug-related AE lasting > 7 days or recurs, with the following exceptions for laboratory abnormalities, drug-related uveitis, pneumonitis, bronchospasm, neurologic toxicity, hypersensitivity reactions, infusion reactions, and endocrinopathies:
  - Grade 3 drug-related uveitis, pneumonitis, bronchospasm, neurologic toxicity, myocarditis, hypersensitivity reaction, or infusion reaction of any duration requires discontinuation.
  - Grade 3 drug-related endocrinopathies adequately controlled with only physiologic hormone replacement do not require discontinuation. Grade  $\geq 3$  adrenal insufficiency requires discontinuation regardless of control with hormone replacement (note: Hospitalization for diagnostic workup of adrenal insufficiency without severe symptoms should not be considered a Grade 3 event).
  - Grade 3 drug-related laboratory abnormalities do not require treatment discontinuation except for the following:
    - ◆ Grade 3 drug-related thrombocytopenia lasting > 7 days or associated with bleeding requires discontinuation
    - ◆ Grade  $\geq 3$  drug-related AST, ALT, or Total bilirubin requires discontinuation
    - ◆ Concurrent AST or ALT > 3 $\times$  ULN and total bilirubin > 2 $\times$  ULN
- \*In most cases of Grade 3 AST or ALT elevation, study drug(s) will be permanently discontinued. If the investigator determines a possible favorable benefit/risk ratio that warrants continuation of study drug(s), a discussion between the investigator and the BMS Medical Monitor/designee must occur.
- Any drug-related Grade 4 endocrinopathy and Grade 3 adrenal insufficiency requires discontinuation.
- Any Grade 4 drug-related AE or laboratory abnormality (including but not limited to creatinine, AST, ALT, or total bilirubin), except for the following events, which do not require discontinuation:
  - Grade 4 neutropenia  $\leq 7$  days
  - Grade 4 lymphopenia or leukopenia
  - Isolated Grade 4 amylase or lipase abnormalities that are not associated with symptoms or clinical manifestations of pancreatitis

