**Table 9.4.4-1: Clinical Laboratory Assessments**

Hematology	
Hemoglobin	
Hematocrit	
Total leukocyte count, including differential	
Platelet count	
Blood type (ABO, Rh, and indirect antiglobulin testing) (screening only)	
Serum Chemistry	
Aspartate aminotransferase (AST)	Albumin
Alanine aminotransferase (ALT)	Sodium
Total bilirubin	Potassium
Alkaline phosphatase	Chloride
Lactate dehydrogenase (LDH)	Calcium
Creatinine a	Magnesium
Blood Urea Nitrogen (BUN) or serum urea level	Creatinine clearance (CLcr)- screening only
Glucose, Phosphate	Carbon Dioxide or Bicarbonate b
	Amylase and lipase: only for participants with pancreatic adenocarcinoma
Urinalysis	
Protein	
Glucose	
Blood	
Leukocyte esterase	
Specific gravity	
pH	
Microscopic examination of the sediment if blood, protein or leukocytes esterase are positive on the dipstick	
Thyroid Function Tests	
TSH (reflex to free T3 and free T4 if abnormal result)	
Serology	
Hepatitis B surface antigen (HBV sAg, Australia antigen), and hepatitis C antibody (HCV Ab) or HCV ribonucleic acid (RNA)HIV-1 and -2 antibody (screening only)	
Other Analyses	
Pregnancy test (WOCBP only: screening, predose, discharge).	
Follicle stimulating hormone (FSH) (screening only for women only)	

a Creatinine clearance measured by 24-hour urine collection or estimated from serum creatinine by the Cockcroft-Gault formula.

b To be done in sites where this is a standard part of the chemistry panel. In sites where testing for CO2/HCO3 is not standard, the test is optional.

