7.5.5 Laboratory Parameters

The analysis population for each laboratory test is restricted to treated subjects meeting that laboratory test abnormality.

A summary as worst CTC grade on-treatment per subject and a by-subject listing of the following laboratory parameters abnormalities will be provided: hemoglobin, hematocrit, leukocytes, platelet count, ALT, AST, alkaline phosphatase (ALP), total bilirubin, lactate dehydrogenase, blood urea nitrogen (BUN) or serum urea level, creatinine, sodium, potassium, calcium, chloride, magnesium, creatinine clearance (CLcr), carbon dioxide or bicarbonate, amylase, glucose, phosphate, albumin, urinalysis labs, serology tests, FSH and lipase.

A summary and a by-subject listing of the following thyroid specific abnormalities will be provided: TSH, FT3, FT4.

A by-subject listing of differences in categorization of SI and US laboratory test results will be provided.

The analyses will be conducted using the 30-day safety window.

In addition, further analyses on specific laboratory parameters will be performed by treatment group:

Abnormal Hepatic Function Test

The number of subjects with the following laboratory abnormalities from on-treatment evaluations will be summarized:

- ALT or AST > 3 x ULN, > 5 x ULN, > 10 x ULN and > 20 x ULN
- Total bilirubin > 2 x ULN
- ALP > 1.5 x ULN
- Concurrent (within 1 day) ALT or AST > 3 x ULN and total bilirubin > 1.5 x ULN
- Concurrent (within 30 days) ALT or AST > 3 x ULN and total bilirubin > 1.5 x ULN
- Concurrent (within 1 day) ALT or AST > 3 x ULN and total bilirubin > 2 x ULN
- Concurrent (within 30 days) ALT or AST > 3 x ULN and total bilirubin > 2 x ULN

Abnormal Thyroid Function Test

The number of subjects with the following laboratory abnormalities from on-treatment evaluations will be summarized:

- TSH value > ULN and
 - with baseline TSH value \leq ULN
 - with at least one FT3/FT4 test value < LLN within 2-week window after the abnormal TSH test
 - with all FT3/FT4 test values \geq LLN within 2-week window after the abnormal TSH test
 - with FT3/FT4 missing within 2-week window after the abnormal TSH test.
- TSH < LLN and
 - with baseline TSH value \geq LLN
 - with at least one FT3/FT4 test value > ULN within 2-week window after the abnormal TSH test
 - with all FT3/FT4 test values \leq ULN within 2-week window after the abnormal TSH test
 - with FT3/FT4 missing within 2-week window after the abnormal TSH test

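### The SAP's on-treatment worst-grade laboratory list names no neutrophil or lymphocyte count, although the differential is collected throughout treatment and worst-grade laboratory abnormalities are part of the primary endpoint

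*SAP*

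**What the plan says.** SAP Section 7.5.5 promises a worst on-treatment CTC grade per subject, with a by-subject listing, for a named set of tests. The set begins "hemoglobin, hematocrit, leukocytes, platelet count, ALT, AST, alkaline phosphatase (ALP), total bilirubin, lactate dehydrogenase" and ends "glucose, phosphate, albumin, urinalysis labs, serology tests, FSH and lipase". Neutrophils and lymphocytes are not named there or elsewhere in the SAP.

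The protocol bears on this in four places.

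- **Collection.** Table 9.4.4-1 has the hematology row "Total leukocyte count, including differential". Table 2.-2 schedules the count with differential weekly in Weeks 1-8, every other week in Weeks 9-24, and every 4 weeks from Week 25.
- **Endpoint and analysis.** The primary endpoint in Table 4.-1 includes specific laboratory abnormalities by worst grade. Section 10.3.2 plans a worst-grade summary of on-study laboratory parameters and names hematology as a class.
- **Dose rules.** Section 7.1.2.1 holds treatment for "Grade 4 hematologic toxicity, except for grade 4 lymphopenia", for febrile neutropenia, and for "Neutropenia with infection, of any grade". Section 8.1.1 exempts "Grade 4 lymphopenia or leukopenia" from the Grade 4 stopping rule. It exempts Grade 4 neutropenia only when it lasts 7 days or less.
- **Screening tests.** Table 9.4.4-1 reads "Creatinine clearance (CLcr)- screening only" and "Follicle stimulating hormone (FSH) (screening only for women only". It also marks the serology row as screening only.

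**The concern.** The primary objective is tolerability, and laboratory worst grade is one of its stated measures. A programmer who builds the tables from SAP 7.5.5 would grade the total leukocyte count but neither of the two differential counts that the protocol's own rules name. Neutropenia and lymphopenia would then be reported only through adverse-event recording. That depends on an action having been taken or on the investigator's judgment, and it is not a systematic reading of every value. The same list asks for an on-treatment grade for tests that the protocol schedules only at screening, which suggests that it was drawn up from Table 9.4.4-1 without the timing notes.

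**Working it through.** There is no figure to reproduce. The check sets the SAP list beside the protocol's collection schedule and rules.

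**1. What the list contains.** SAP 7.5.5 names 26 entries, with thyroid tests separate. The blood-count entries are hemoglobin, hematocrit, leukocytes and platelets: 4 of 26. Differential counts named: 0.

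**2. What is collected.** Table 2.-2 gives up to 8 counts with differential in Weeks 1-8, and 16/2 = 8 more in Weeks 9-24. That is up to 16 per participant in the first 24 weeks, each carrying a neutrophil and a lymphocyte value.

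**3. Whether a total count can stand in.** Protocol Section 6.1 (criterion 2j) sets separate thresholds of 2000/µL for WBC and 1500/µL for neutrophils. A participant with a total of exactly 2000/µL meets the first. That participant meets the second only if at least 1500/2000 = 75% of the cells are neutrophils. The total does not fix the neutrophil count, so it does not fix the neutrophil grade, and the same holds for lymphocytes.

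**4. Role of each count in the dose rules.**

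| Protocol rule | Neutropenia | Lymphopenia |
|---|---|---|
| 7.1.2.1, febrile neutropenia | trigger | not named |
| 7.1.2.1, neutropenia with infection | trigger | not named |
| 7.1.2.1, Grade 4 hematologic toxicity | trigger, as part of the class | exempt (Grade 4) |
| 7.1.1.1, Grade 3 drug-related laboratory abnormality | not exempted | exempt (Grade 3) |
| 8.1.1, Grade 4 drug-related event | trigger if longer than 7 days | exempt (Grade 4) |

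Neutropenia can trigger all five rules. Lymphopenia triggers none, and the three rules that name it exempt it. In Section 8.1.1, Grade 4 leukopenia is exempt as well. For that rule, the SAP grades a count that the rule sets aside and omits the one it uses.

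**5. What still reaches the report.** Protocol Section 9.2.6 requires an adverse-event record for a laboratory abnormality that is clinically significant or serious, that led to interruption or discontinuation of treatment, or that needed specific corrective therapy. SAP 7.5.2 to 7.5.4 tabulate serious events, events leading to discontinuation and all adverse events by worst CTC grade. Neutropenia that set off a hold or a stop is therefore captured. Neutrophil and lymphocyte values that met none of these conditions are not.

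**6. Listed tests without a scheduled on-treatment value.** SAP 6.1 treats a laboratory evaluation as on-treatment only if it was taken after first dose. Creatinine clearance, serology and FSH are marked screening only in Table 9.4.4-1. Urinalysis carries no such mark, but it appears in Table 2.-1 and has no row in the visible text of Tables 2.-2 and 2.-3. That makes 3 + 1 = 4 of 26 entries. SAP 7.1.2 describes the laboratory scope as hematology, chemistry and thyroid tests, which does not include urinalysis, serology or FSH.

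**The case against.** The strongest reply is that the leukocyte entry is shorthand. The SAP list largely follows Table 9.4.4-1, where the total count and the differential share one row, so its author may have meant the whole row. SAP 7.1.2 says hematology will be evaluated, and the Data Presentation Plan, which holds the mock-ups and is not available here, may show both counts. This is plausible, and it means the omission may be one of wording and not of intent. It does not rescue the text: the SAP drops the reference to the differential, and a leukocyte row gives neither grade. A reader might also infer from Table 9.4.4-1 that the protocol treats the two as distinct content. It does not, and the point does not need that reading.

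A second reply is that neutropenia that matters clinically will appear as an adverse event. This largely stands. A reader might infer that the report would contain no neutropenia, or only what an investigator judged clinically significant. Protocol 9.2.6 rules out both readings, because interruption, discontinuation and corrective therapy also require a record.

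A third reply concerns the screening-only tests. Empty rows bias nothing, and unscheduled tests are permitted. Creatinine clearance could be computed on treatment, since creatinine and weight are both collected on study and Section 10.3.2 asks for renal function by worst grade. All of this stands, so that part is housekeeping.

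**Conclusion.** SAP 7.5.5 is wrong as written. Its worst-grade list omits neutrophil and lymphocyte counts that are collected throughout treatment and fall within the protocol's planned hematology summary and primary endpoint.

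The size is two missing rows in the summary and listing for each of the three cohorts. Forty treated participants were planned per cohort, but the SAP reports that the combination was discontinued before 20 were treated in the NSCLC cohort. How many participants have a graded value that would go unreported cannot be worked out from the documents.

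A reader might infer that both counts drive the dose rules. Only neutropenia does. The case for lymphocytes rests on the endpoint, the planned hematology summary and the fact that the data exist. The exemptions add a little to it: lymphopenia that is exempt from a hold is less likely to reach the adverse-event tables through an interruption.

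The conclusion assumes that the list is applied literally. If the mock-ups already show both counts, only the SAP wording needs correcting. The screening-only observation is firm for FSH and serology. It is firm for creatinine clearance unless a derivation is intended, and slightly less certain for urinalysis because the text of Table 2.-2 is partly cut. It changes no result.

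**What to change.** In SAP 7.5.5, add absolute neutrophil count and absolute lymphocyte count to the worst-CTC-grade on-treatment summary and to the by-subject listing, and bring the mock-ups into line if they differ.

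As housekeeping in the same edit, move serology, FSH and urinalysis to a baseline listing. For creatinine clearance, either list it at baseline or state how an on-treatment value is derived from creatinine and weight.

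The cost is two table rows from data already collected and a short change of SAP wording. No visit, sample or procedure changes.

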**Table 2.-2: On Study Procedural Outline (CA2099GW)**

Procedure	Local Lab (LL) or Central Lab (CL)	Weeks 1-8		Weeks 9-24 Q2W	Week 25 and beyond Q4W	Notes Procedure Window $\pm 2$ Days Unless Specified Otherwise
		Weeks 1, 3, 5, 7	Weeks 2,4,6, 8			
Laboratory Tests						
Pregnancy Test	LL	X Weeks 1 and 5		X	X	To be done within 24 hours of first dose of study therapy, and then at least once every 4 weeks (+/-1 week) regardless of dosing schedule.
CBC with Differential and Platelets	LL	X	X	X	X	Weeks 1-8: every week Weeks 9-24: every other week Week 25 and beyond: every 4 weeks
Serum Chemistry	LL	X		X	X	Weeks 1-24: every other week Week 25 and beyond: every 4 weeks  Chemistry panel includes LDH, AST, ALT, ALP, albumin, total bilirubin, BUN or serum urea level, creatinine, Ca, Mg, Na, K, Cl, glucose, phosphate, carbon dioxide or bicarbonate.  Amylase and lipase: only for participants with pancreatic adenocarcinoma.

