6.3 Populations for Analyses

- All Enrolled subjects: All subjects who signed the informed consent form and obtained a subject number.
- All Treated subjects: All enrolled subjects who received at least one dose of any study treatment. This will be both efficacy and safety population.
- Subjects Entered Follow-up: All subjects who entered the follow-up period as specified in subject status CRF pages.
- All Treated Subjects with Objective Response: All treated subjects with response of CR or PR per RECIST v1.1 per Investigator.

Unless otherwise specified, the efficacy and safety analyses will include all treated subjects.

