7 STATISTICAL ANALYSES

7.1 General Methods

Unless otherwise noted, discrete variables will be tabulated by the frequency and proportion of subjects falling into each category, grouped by treatment. Percentages given in these tables will be rounded to the first decimal and, therefore, may not always sum to 100%. Percentages less than 0.1 will be indicated as '< 0.1'. Continuous variables will be summarized by treatment group using the mean, standard deviation, median, minimum, and maximum values.

Time-to-event variables (e.g. time-to resolution) will be analysed using the Kaplan-Meier technique. When specified, the median will be reported along with 95% CI using Brookmeyer and Crowley method¹ (using log-log transformation for constructing the confidence intervals²).

The conventions to be used for imputing missing and partial dates for analyses requiring dates are described in [Section 8](#).

All analyses would be presented by tumor type:

- Triple negative breast cancer (TNBC)
- Non-small cell lung cancer (NSCLC)
- Pancreatic adenocarcinoma cancer (PAC).

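### SAP 7.5.5 summarises amylase and lipase by tumor type although the protocol schedules them only for the pancreatic cohort, and its stated laboratory population gives no usable denominator

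*SAP*

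**What the plan says.** SAP 7.5.5 calls for a summary of worst on-treatment CTC grade per subject, plus a by-subject listing, for a long list of tests that ends "carbon dioxide or bicarbonate, amylase, glucose, phosphate, albumin, urinalysis labs, serology tests, FSH and lipase". No test in the list is limited to a cohort or a site. SAP 7.1 adds: "All analyses would be presented by tumor type", naming TNBC, NSCLC and PAC.

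The protocol is narrower. The serum chemistry row of Table 2.-2 carries the note "Amylase and lipase: only for participants with pancreatic adenocarcinoma". The same restriction stands in Table 2.-1 (screening), Table 2.-3 (follow-up) and Table 9.4.4-1.

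Bicarbonate is treated differently. It is the named alternative to carbon dioxide in the routine panel for everyone ("Chemistry panel includes LDH, AST, ALT, ALP, albumin, total bilirubin, BUN or serum urea level, creatinine, Ca, Mg, Na, K, Cl, glucose, phosphate, carbon dioxide"), subject to footnote b of Table 9.4.4-1: "To be done in sites where this is a standard part of the chemistry panel". At other sites it is optional.

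On the population, SAP 6.3 sets a default: "Unless otherwise specified, the efficacy and safety analyses will include all treated subjects". SAP 7.5.5 then specifies otherwise: "The analysis population for each laboratory test is restricted to treated subjects meeting that laboratory test abnormality".

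**The concern.** The incidence of specific laboratory abnormalities by worst grade is part of the primary endpoint (protocol Synopsis and Table 4.-1). A table built as SAP 7.5.5 and 7.1 direct would have amylase and lipase rows under TNBC and NSCLC, where the protocol does not plan the tests.

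Three things are at stake.

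- **No incidence.** A TNBC or NSCLC row would describe an unknown, self-selected subset of participants.
- **No comparability.** PAC participants have chemistry every 2 weeks to Week 24 and every 4 weeks afterwards. Under protocol Section 6.1 they may also enter with amylase or lipase above 1.5 x ULN if there are no signs of pancreatitis. Columns side by side would differ because of testing and entry rules, whatever the treatment does.
- **No usable denominator.** SAP 7.1 tabulates discrete variables as frequency and proportion, so every row needs a denominator. The one stated in 7.5.5 is the set of subjects who already have the abnormality.

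**Working it through.** **Step 1. Schedule against summary.**

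| Place | Amylase and lipase | Carbon dioxide or bicarbonate |
|---|---|---|
| Protocol Table 2.-1, screening | PAC only | In panel, all cohorts |
| Protocol Table 2.-2, on study | PAC only | In panel, all cohorts |
| Protocol Table 2.-3, follow-up | PAC only | In panel, all cohorts |
| Protocol Table 9.4.4-1 | PAC only | Depends on site practice (footnote b) |
| SAP 7.5.5 with 7.1 | All three tumor types | All three tumor types |

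Scheduled on-treatment coverage for amylase and lipase is therefore 100% of PAC and 0% of TNBC and NSCLC.

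**Step 2. Where a TNBC or NSCLC value could come from.** Protocol Section 9.4.5 allows tests outside the study schedule on clinical indication or where local rules demand them. Section 9.4.4 obliges sites to provide the results of protocol-required tests only. The number tested off schedule, and the share of those results that reaches the database, cannot be known from the documents. Both may be zero.

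**Step 3. What the row would show.** Let N be treated, m tested and x abnormal. The possible proportions are x/m, x/N and, under the literal 7.5.5 population, x/x. The documents give no m or x, so the values below are assumptions, with N = 40.

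| m tested | x abnormal | x/m | x/N | x/x (7.5.5 as worded) |
|---|---|---|---|---|
| 3 | 2 | 66.7% | 5.0% | 100% |
| 8 | 3 | 37.5% | 7.5% | 100% |
| 8 | 4 | 50.0% | 10.0% | 100% |
| 10 | 4 | 40.0% | 10.0% | 100% |

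The x/x column is 100% for any x above zero and undefined at x = 0. This applies to every test in the section, and to PAC as well.

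**Step 4. The plan's own detection figure.** SAP Section 5 gives more than 87% probability of seeing an event with a true rate of 5% in 40 participants. This reproduces: 1 - 0.95^40 = 0.8715. It requires all 40 to be observed. If only m of 40 were tested, and at random, the probability would be:

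- m = 0: 0
- m = 5: 1 - 0.95^5 = 0.226
- m = 10: 1 - 0.95^10 = 0.401
- m = 20: 1 - 0.95^20 = 0.642

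Unscheduled tests are not a random sample, so these figures only show that the 87% cannot be carried over to amylase and lipase in TNBC. In NSCLC the SAP's Schedule of Analyses says that the combination was stopped before 20 were treated, so n = 40 does not apply there at all.

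**The case against.** The strongest reply is that little harm can follow. The TNBC and NSCLC rows may be empty, because sites need not send unscheduled results. No p-value, decision rule or formal comparison between cohorts rests on the table, and the report is a synoptic close-out. Under protocol Section 9.2.6, laboratory abnormalities that are clinically significant, stop or interrupt treatment, or need corrective therapy are also recorded as adverse events, which SAP 7.5.4 tabulates. Table layout belongs to the Data Presentation Plan (SAP Section 9), which is not available here and might already show the number tested.

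Most of this stands, and it limits the size of the point. It does not remove it. Adverse event records do not repair the laboratory row, and a layout document cannot be assumed to override the population that the SAP states.

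A reader might infer four stronger things that the documents do not support.

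- **That the denominator is all treated, so a near-zero row would pass for absence of toxicity.** SAP 7.5.5 sets its own population and displaces the all-treated default of 6.3.
- **That every TNBC or NSCLC value was ordered on suspicion.** That is one route. Local requirements are another, and the documents do not say which would dominate.
- **That bicarbonate has the same fault.** It is routine chemistry in all three cohorts. Its gaps depend on the site, occur in PAC too, and have nothing to do with suspicion.
- **That a contrast such as 67% against 5% measures the bias.** It is one assumed scenario among those in the table of assumed values.

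**Conclusion.** The mismatch is real. The SAP directs a by-tumor-type summary of amylase and lipase, and the protocol schedules neither test outside PAC. In two of three cohorts the row cannot estimate an incidence and should not be read beside PAC. The population sentence is a second fault in the same section: taken literally it yields 100% wherever anyone is abnormal. A kinder reading, that it was meant to say subjects with a result for the test, is plausible, but it is not what is written.

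The impact is modest. It touches part of the primary endpoint, but through descriptive safety reporting only. The conclusion rests on the protocol schedules and the SAP text. It needs no assumption about how many unscheduled tests were done; the size of any distortion would depend on that number, which the documents do not give.

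**What to change.** In SAP 7.5.5:

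- Limit the amylase and lipase worst-grade summary to PAC. Give any TNBC or NSCLC values in the by-subject listing only, marked as not scheduled.
- Replace the population sentence with: *treated subjects with at least one on-treatment result for that test*. Show that number for each test and cohort.

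The second change also deals with bicarbonate, since the number tested will reveal the gaps left by site practice. It will equally expose tests in the same list that Table 9.4.4-1 marks as screening only, such as FSH and creatinine clearance, for which no on-treatment result is scheduled.

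The cost is SAP and table-shell wording, with no new data and no protocol change. The downside is that two cohorts lose a summary row, but that row could not have been interpreted.
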